### 3. Study Design

As mentioned in section 2, this project consists of two distinct aims: aim 1 (usability) and aim 2 (RCT). Aim 1 of this project will be conducted within a population of 5 to 15 healthy volunteers using a single study visit lasting approximately 30 to 60 minutes in which they will be asked to provide feedback on the app and its contents. Individuals enrolled into this aim will be asked to provide feedback via written communication. Feedback will be used to improve the app for Aim 2 (RCT).

Aim 2, which is the main focus of this exploratory pilot randomized clinical trial (RCT) is to be conducted within a population of 60 cardio-respiratory survivors with a 3-month follow-up. Eligible patients will be those individuals who are admitted to the hospital and receive treatment for cardio or respiratory failure. Additional characteristics of the target population are those that exhibit high psychological distress, as defined by their scoring at the time of hospital discharge via the Hospital Anxiety and Depression Scale (HADS) and Post Traumatic Stress Scale (PTSS) surveys. Eligible patients will be identified via daily electronic medical record (EMR) review and approached for consent while still hospitalized. Patients will be

asked to complete app registration and baseline survey completion post-consent, but at the time of hospitalization, if possible. Upon discharge, patients will be asked to complete survey 1, T1, to assess their levels of psychological distress. Should the patient demonstrate high enough levels of psychological distress, they will be randomized to 1 of 3 treatment arms:

- Arm 1: mCST Intervention Group 1 (self-directed coping skills training app with CST therapist intro call)
- Arm 2: mCST Intervention Group 2 (self-directed coping skills training app only)
- Arm 3: usual care (control group; no CST therapist and no coping skills training app)

Each participant, regardless of randomization arm will be asked to complete the following surveys at the listed time points below:

- Baseline (during hospitalization, post consent)
  - Collect sociodemographic data and establish baseline psychological distress.
- T1 (at the time of hospital discharge, within 1 week of returning to home but no more than 1 month (30 days) from discharge)
  - Complete the HADS, PTSS, and PHQ-10, QOL 100-point visual analog scale, IADL/ADLs
- T2 (1 month (30 days) post date of discharge; up to 2 months (60 days) for completion)
  - Complete the HADS, PTSS, and PHQ-10, QOL 100-point visual analog scale, IADL/ADLs
- T3 (3 months (90 days) post date of discharge; up to 4 months (120 days) for completion)
  - Complete the HADS, PTSS, and PHQ-10, QOL 100-point visual analog scale, IADL/ADLs, CSQ-8

Additionally, each participant, regardless of randomization arm, will be asked to complete a weekly HADS survey during the first month (30 days) of study participation, post discharge. The purpose of this survey is to assess overall psychological distress.

For those patients who are assigned to arms 1 or 2, they will be asked to utilize the app for 1 month (28 days). During that 1 month time period, they will be provided with weekly coping skills, as listed below:

- *Week 1: Progressive Muscle Relaxation and Pleasant Imagery*
  - Week 1 includes two coping skills: progressive muscle relaxation and pleasant imagery. Progressive muscle relaxation is the practice of taking time to enjoy the *feeling* of relaxation, whereas the practice of pleasant imagery is using one's imagination to create a pleasant or happy scene, like a pleasant daydream, that they can return to at any moment.
- *Week 2: Pleasant Activities and activity-Rest Cycling*
  - Week 2, like week 1, includes two coping skills: pleasant activities and activity rest cycling. Pleasant activities is intended to help one *plan* to do regular activities by 1) convincing one's self to find time and effort to complete the activity/ies they enjoy, 2) develop a schedule to help them commit to completing the activity/ies, and 3) encourage one to hold themselves and have others help hold them accountable to complete the activity/ies. Activity rest cycling is a practice in which one learns to overcome "over activity", meaning doing too much at one time or over doing a particular activity. There are 3 components to practicing activity rest cycling: 1) identify activities that one may over-do, 2) take note of how one feels after the activity is completed, and 3) set time limitations on how long one will perform the activity.
- *Week 3: Fast Relax and Managing Negative Thoughts*
  - Week 3 includes two coping skills: Fast relax and managing negative thoughts. The purpose of fast relax is to help one keep feelings, such as pain or tension levels, low throughout the day by allowing one's self to be still and breath fully for a few seconds to a minute. Managing negative thoughts encourages individuals to understand that having negative thoughts is okay and normal; the practice encourages one to notice their negative thoughts,

such as worry, anger, stress, and then teaches them to take control of the thought(s) and then change the thought to be more positive.

- **Week 4: Problem Solving and Maintenance**
  - *Week 4 includes one additional coping skill: problem solving. Problem solving is a skill that helps an individual focus on one problem at a time and teaches them to 1) recognize what the problem is, 2) understand why there is a problem, and 3) help them think about what they can do to solve the problem. Additionally, during week 4, individuals are instructed on how to maintain the coping skills learned during the previous 3 weeks and are encouraged to practice the skill(s) that worked best for them.*

At the beginning of each week, a brief introduction video explaining the study will be provided. During each week's exercise, patients will have the opportunity to listen to pre-recorded visual audios of physicians and patients describing their own, personal coping mechanisms related to each week's skill.

The native app will track fidelity and adherence by way of automated prompts and the use of an interactive dashboard for administrative users (i.e., study team) to track individual patient use. Should a patient stop responding to the app (e.g., stop using it for any period of time), the study team may contact the patient to remind him/her of their commitment to the study and the importance of compliance.

For those individuals in arm 3, they will receive neither therapist nor app-directed intervention. The study team will administer the weekly surveys during the first month (30 days) via email and/or phone, and at T1, T2, and T3.

The study will be conducted at Duke University Hospital (DUH) and Durham Regional Hospital (DRH).

#### **4. Study Objectives, Hypotheses, and Outcomes**

The overall objective of the pilot RCT is to determine the feasibility, acceptability and clinical impact of the intervention on patients' 1- and 3-month psychological distress symptoms of a self-directed mobile coping skills training (mCST) intervention, known as "Blueprint" as compared to usual care control.

The primary hypothesis in which this study is based is that the mCST will be feasible and acceptable based on comparison of observed to priori benchmarks.

The second hypothesis is compared to usual care, the mCST use by enrolled subjects will lead to improvement in symptoms of psychological distress via the HADS and PTSS at the 1- and 3-month mark post randomization.

The primary outcome of the pilot RCT is centered on acceptability and feasibility. The Client Satisfaction Questionnaire 8 will measure acceptability with open-ended participant feedback completed at the time of T3, which is considered end of study (EOS). Feasibility will be measured by frequency of randomization, retention, and adherence. Secondary outcomes are HADS and PTSS scores at 1 and 3 months post-randomization.

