## Study Visits

For aim 1, each participant will be asked to complete a singular study visit that last approximately 30-60 minutes. During this study visit, post consent, the individual will be asked to do the following:

- Find and install the Pattern Health app
- Register to the Blueprint study
- Complete baseline survey
- Randomize to 1 of 3 arms or screen fail purposely
- Provide feedback on app content and usability.

For aim 2, each consented patient will be asked to complete up to four individual study visits.

- **Baseline:** this visit is to occur post-consent (same day, ideally) at the time of hospital admission just prior to discharge. However, this visit may occur at the time of hospital discharge within 1-3 days of returning to home. At this visit, the following will occur:
  - App Registration
  - Baseline Survey Completion
- **T1 (Day 0) (+30 days):** this visit is to occur at the time of hospital discharge to home, ideally within the first week (7 days) of returning to home; however, it can occur up to 1 month (30 days) from the time of hospital discharge to home. At this visit, the patient will complete the T1 survey via the app, which includes the HADS, PTSS, and PHQ-10 surveys. Score dependent, the patient will be randomized to 1 of 3 arms: Group 1 (Blueprint app), Group 2 (Blueprint app + therapist), and Group 3 (control; no Blueprint app and no therapist). If the patient's psychological distress score is too low; he/she will receive an automated alert via the app describing they are not eligible and their study participation is complete.
- **T2 (Day 30) (+60 days):** this visit is to occur post 1 month randomization for those patients who remain eligible to participate in the study. HADS, PTSS, and PHQ-10 surveys will be administered again. If the patient's survey scores indicate high levels of distress, as defined by a triggered SI alert or increased distress score from T1, a delegated study team member will contact the patient for safety precautions.

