- Very frequently
- Somewhat frequently
- Somewhat infrequently
- Very infrequently
- Almost never

101. I'm finding myself doing things without paying attention.

Response is \*\*one\*\* of:

- Almost always
- Very frequently
- Somewhat frequently
- Somewhat infrequently
- Very infrequently
- Almost never

102. Please help us improve the Blueprint program by answering some questions about it. We are interested in your honest opinion, whether positive or negative.

(This is an information screen that requires no response)

Click Next to continue.

103. How would you rate the quality of the Blueprint program?

Response is \*\*one\*\* of:

- Excellent
- Good
- Fair
- Poor

104. Did you get the kind of program that you wanted?

Response is \*\*one\*\* of:

- Yes, definitely
- Yes, generally
- No, not really
- No, definitely not

105. To what extent has the Blueprint program met your needs?

Response is \*\*one\*\* of:

- Almost all of my needs have been met
- Most of my needs have been met
- Only a few of my needs have been met
- None of my needs have been met

106. If a friend were in need of similar help, would you recommend the Blueprint program to him or her?

Response is \*\*one\*\* of:

- Yes, generally

- Yes, generally
- No, not really
- No, definitely not

107. How satisfied are you with the amount of help you received in the Blueprint program?

Response is **\*\*one\*\*** of:

- Very satisfied
- Mostly satisfied
- Indifferent or mildly dissatisfied
- Quite dissatisfied

108. Has the Blueprint program helped you to deal more effectively with your problems or stresses?

Response is **\*\*one\*\*** of:

- Yes, it helped a great deal
- Yes, it helped somewhat
- No, it really didn't help
- No, it seemed to make things worse

109. In an overall, general sense, how satisfied are you with the Blueprint program?

Response is **\*\*one\*\*** of:

- Very satisfied
- Mostly satisfied
- Indifferent or mildly dissatisfied
- Quite dissatisfied

110. If you were to decide about participating or not in the Blueprint program, would you do it again?

Response is **\*\*one\*\*** of:

- Yes, definitely
- Yes, I think so
- No, I don't think so
- No, definitely not

111. Could you provide any comments about specific ways the Blueprint program helped or didn't help you?

Response is **\*\*free-form text\*\***.

112. Click Next to submit your answers and see your results.

(This is a score screen that requires no response)

113. Thank You!

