100. I'm finding myself preoccupied with the future or the past.

Response is \*\*one\*\* of:

- Almost always
- Very frequently
- Somewhat frequently
- Somewhat infrequently
- Very infrequently
- Almost never

101. I'm finding myself doing things without paying attention.

Response is \*\*one\*\* of:

- Almost always
- Very frequently
- Somewhat frequently
- Somewhat infrequently
- Very infrequently
- Almost never

102. Click Next to submit your answers and see your results.

(This is a score screen that requires no response)

103. Thank You!

(This is an information screen that requires no response)

Please click Next to exit the survey.

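### CSQ-8 is scheduled for T3 but printed only in the T2 survey, and SAP 4.1 and Table 2 do not carry the feasibility targets through to a comparison

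*Protocol*

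**What the plan says.** **CSQ-8 timing.** Protocol section 4 makes acceptability and feasibility the primary outcome and states "The Client Satisfaction Questionnaire 8 will measure acceptability with open-ended participant feedback completed at the time of T3". The survey list in Protocol section 3 agrees. Its T3 entry reads "Complete the HADS, PTSS, and PHQ-10, QOL 100-point visual analog scale, IADL/ADLs, CSQ-8", and its T2 entry has the same list without CSQ-8.

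**The printed surveys.** In Appendix 3 H (T2 Survey) a block opens with "Please help us improve the Blueprint program by answering some questions about it". Eight satisfaction items follow (103 to 110), then item 111, "Could you provide any comments about specific ways the Blueprint program helped". In Appendix 3 I (T3 Survey) the last question is mindfulness item 101, followed by "102. Click Next to submit your answers and see your results" and a thank-you screen.

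**Feasibility.** Protocol section 4 says "Feasibility will be measured by frequency of randomization, retention, and adherence". Protocol section 9 plans t-tests and chi-square tests of observed values against benchmarks among mCST recipients. SAP 1.2.1 rests primary hypothesis 1 on the same comparison. SAP 3.1 lists five targets: eligibility 70%, consent 80%, randomization 80%, retention 80% and adherence 75% of tasks. It adds a note that they need sharper definition. SAP 4.1 says only that CSQ-8 and SUS scores will be evaluated and reported in Table 2.

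**The concern.** There are two breaks between the stated primary outcome and what the plan would deliver.

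First, a team that follows Appendix 3 as printed collects CSQ-8 and the open feedback at T2 and obtains neither at T3, the stated time. The two times mean different things. T2 falls just after the 28-day app course, whereas T3 is end of study.

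Second, a statistician who follows SAP 4.1 and fills in Table 2 exactly will not have set any result against its target. The table will also contain no figure that answers the adherence or eligibility target. This pilot exists to inform a definitive trial through those comparisons. If the rule for meeting a target is chosen after the results are seen, the primary conclusion becomes a matter of discretion.

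**Working it through.** The documents give no calculation to reproduce, so the main check sets the passages side by side.

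**1. CSQ-8 and open feedback**

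| Source | T2 | T3 |
|---|---|---|
| Protocol section 3, survey lists | not listed | CSQ-8 listed |
| Protocol section 4 | – | CSQ-8 and open feedback |
| Protocol, Study Visits | not named | not named |
| Appendix 3, printed surveys | 8 items (103–110) + comment box (111) | 0 items, no comment box |
| SAP 3.1, CSQ-8 row | no time point | no time point |

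The T3 survey is numbered without a break from 1 to 103, so the missing block is not a gap left by text extraction.

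**2. Item 106.** Of its four printed responses, the first two are the same mid-positive answer. The top response is therefore missing from one of the eight items that make up the total.

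**3. SAP 3.1 targets against SAP Table 2**

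| Target or measure | Row in Table 2? | Set beside its target? |
|---|---|---|
| Eligibility 70% | no | no |
| Consent 80% | yes | no |
| Randomization 80% | yes | no |
| Retention 80% | yes | no |
| Adherence 75% of tasks | no | no |
| SUS (sent to Table 2 by SAP 4.1) | no | no target given |

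Three of the five targets have a row, and none has a comparison.

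**4. Why the all-components row cannot stand in for adherence (illustration).** Assume that the target means average task completion per participant, that this average is exactly 75%, and that components are the same items as tasks. If everyone completes three quarters of the tasks, 0% complete all of them. At the other extreme, a share *s* completes everything and the rest almost nothing, so *s* is at most 75%: 0.75 × 50 = 37.5, hence 37 of 50, or 0.75 × 30 = 22.5, hence 22 of 30. The row could show anything from 0% to about 75% with the target exactly met.

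**5. What an unstated rule does to retention (illustration).** Inputs are the 80% target and a two-sided 5% level (assumed). The denominators are mCST recipients, 25 + 25 = 50 (protocol) or 15 + 15 = 30 (SAP), or all arms, 60 or 45. The one-sample chi-square without continuity correction is z², with z = (x/n − 0.80) / √(0.80 × 0.20 / n).

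- n = 50: 34 gives z = −2.12, p = 0.034; 35 gives z = −1.77, p = 0.077; 46 gives z = 2.12, p = 0.034.
- n = 30: 19 gives z = −2.28, p = 0.022; 20 gives z = −1.83, p = 0.068; 29 gives z = 2.28, p = 0.022.
- n = 60: 41 gives z = −2.26, p = 0.024; 42 gives z = −1.94, p = 0.053.
- n = 45: 30 gives z = −2.24, p = 0.025; 31 gives z = −1.86, p = 0.062.

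| Possible rule for meeting 80% | n = 50 | n = 30 |
|---|---|---|
| Not significantly below | from 35 | from 20 |
| Estimate at or above target | from 40 | from 24 |
| Significantly above | from 46 | from 29 |

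If retention is counted over all arms, the first rule starts at 42/60 or 31/45.

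**The case against.** Three arguments deserve weight.

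- **Nothing need be lost.** A reader might infer that the primary acceptability outcome will not be collected. The documents do not support that. The full block is printed at T2, just after the app course, and those data would be usable. The appendix is also visibly imperfect: the T1 survey jumps from item 63 to item 78, and a Week 2 heading sits over a second Week 1 check-in. The live app may therefore differ from it. This argument stands. The printed contradiction is certain, but its effect on the data is not.
- **Targets and tests do exist.** A reader might infer that the trial has no benchmarks. It has five, in SAP 3.1, and Protocol section 9 names the tests and the population. The SAP itself flags the targets as unfinished. This also stands, and the defect is one of carry-through. Nor does the SAP's remark against p-values cancel the benchmark tests. It sits in SAP 4.2 and concerns HADS and PTSS, so applying it to Aim 1 is inference.
- **The figures rest on unstated rules.** No document states a rule for meeting a target, fixes the retention denominator, or says that 75% of tasks is an average. It could equally mean the share of participants reaching 75%. Table 2 lays retention out by arm, control included. So the retention and adherence figures are illustrations only. Nor does any document say that the all-components row was meant as the adherence measure.

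None of this removes the two documentary facts: the time points contradict each other, and Table 2 cannot show whether the adherence or eligibility target was reached.

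**Conclusion.** The plan is wrong as written on both counts and should be fixed.

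The CSQ-8 timing contradiction and the missing Table 2 content follow directly from the texts, without any assumption about sample size, error rate or variability. The item 106 defect is equally plain in print, but whether it exists in the app is unknown.

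The practical size is moderate. Acceptability would be measured at a different time from the one stated rather than not at all. Two of five feasibility targets would have no reported figure, and the other three no stated comparison. Under the assumed rules, results from 35 to 39 of 50, or 20 to 23 of 30, would pass one reasonable rule and fail another. That shows why a rule is needed, not which rule is right.

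The absence of a CSQ-8 target in SAP 3.1 is missing detail for the authors to settle, and the conclusion does not depend on it.

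**What to change.** Before outcome data are examined:

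(a) **Check the live app, then reconcile the CSQ-8 time point** across Protocol sections 3 and 4, Appendix 3 H and I, and SAP 3.1. If the items were live at T3, correct Appendix 3. If they are at T2 and collection is open, move them to T3. If they were collected at T2, restate CSQ-8 as a T2 outcome and report actual days to completion. Actual days are needed because the T2 window is given as "T2 (1 month (30 days) post date of discharge; up to 2 months (60 days) for completion" in Protocol section 3 but as "T2 (Day 30) (+60 days", counted from randomization, under Study Visits. Check item 106 in the app and, if the defect is real, state how it is scored.

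(b) **Complete SAP 4.1 and Table 2.** Add:
- an adherence row: completed over assigned app tasks per participant over 28 days in Arms 1 and 2, with mean, SD and 95% CI beside 75%;
- an eligibility row;
- a SUS row, or drop SUS from SAP 4.1;
- a benchmark column, with n/N, percentage, exact 95% CI and the stated denominator for each proportion.

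Keep the all-components row as descriptive only.

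(c) **State in SAP 4.1 whether the Protocol section 9 tests among mCST recipients still apply, and which result counts as met.** If they are dropped, amend section 9 or record the departure.

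The cost is wording in SAP 3.1 and 4.1, up to three rows and one column in Table 2, and possibly a sentence in Protocol section 9. A survey edit is needed only if collection is still open. SAP 2.2 mentions criteria applied after data collection, so it may already be closed. Participants carry no extra burden, since the same nine questions are asked once either way.

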- **Withdraw by PI or Self:** defined as any individual who voluntarily consents to participate in the study, but is then withdrawn from the study. The PI may withdraw a participant at any time without their consent if the PI deems it is in their best interest to no longer participate OR the patient demonstrates continuous lack of compliance with study protocol and study procedures. Additionally, if the patient is re-admitted to the hospital during the time of randomization, he/she will be withdrawn from the study by the PI. The study team may re-enroll the patient at the time of discharge following the same screening procedures. The patient may withdraw themselves at any time; the study team will be asked to document the reason for withdraw for study records. Patients who reach this status have no additional follow-ups or study requirements. Patients who are assigned this status must be maintained on the enrollment log.
- **Lost to Follow-Up (LTF):** defined as any individual who voluntarily consents to participate in the study but after non-compliance and at least 3 documented, attempted contacts appropriately spaced 1-5 days apart, the individual will be considered LTF.
  - For aim 2 only:
    - Patients who reach this status have no additional follow-ups or study requirements. Patients who are assigned this status must be maintained on the enrollment log.
    - A patient who returns the study team's contacts within 1 week of last attempted contact may resume study participation.
- **Completed:** defined as any individual who both consented and randomized to the study and completed T1-T3 (aim 2 only) or any individual who completed assigned study visit (aim 1 only). Individuals who reach this status have no additional follow-up or study requirements. Individuals who are assigned this status must be maintained on the enrollment log.

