#### Withdraw While in Study

If an individual states that they wish to drop out, the study team will respect that as well. A follow-up question may be asked to ascertain the reason for withdraw; however, this is for documentation purposes only.

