3.3 Other Variables of interest

Variable	Dataset	Description	Specifications

4 Statistical Analysis Plan

All analyses will be done using SAS 9.4. Continuous variables will be summarized with mean/standard deviation/median/Q1-Q3/range and categorical variables with frequency counts and percentages. Number of missing data for each variable will be reported.

4.1 Analysis Plan for Primary Aim 1

1. First, we will describe our cohort. In Table 1 we will summarize participant characteristics overall and by arm. No statistical tests will be provided as this was a randomized trial, and ideally groups should be balanced.
2. To assess Aim 1 for feasibility and acceptability we will evaluate CSQ-8 and SUS scores. Results will be reported in Table 2.

4.2 Analysis Plan for Primary Aim 2

1. To address Aim 2, we will describe the secondary outcomes at each time point by arm, as well as the change in scores at T2 and T3 from T1 in Table 3. Any additional secondary outcomes will be described in this table.
2. To assess if there was change at each timepoint of interest between the arms we estimate mean changes (and 95% CI) from baseline to each timepoint for each distress outcome (HADS, PTSS) using a general linear model (PROC MIXED). Model parameters will include treatment arm (1, 2, 3), time indicator (T1, T2, T3), and an arm by time interaction term. Change estimates and CI's will be reported in Table 4. To quantify clinically important differences, rather than report p-values which is not recommended for pilot studies with

small sample sizes, we will compare the estimated group mean differences and 95% CI's to half (0.5) of the baseline standard deviation (SD) of each outcome score.

5 Appendix I: Planned figures and tables

Figure 1: CONSORT Diagram

Table 1: Demographic characteristics of participants at baseline

Characteristic	Arm 1: Intervention Group 1 (Blueprint + Therapist) N=	Arm 2: Intervention Group 2 (Blueprint only) N=	Arm 3: Control (Usual Care) N=	Total N=
Stratification Variables				
Age				
<50				
≥50				
ICU Service				
Medical				
Surgical				
Baseline HADS				
<14				
≥14				
Other Baseline Characteristics				
Age				
Mean (sd)				
Median				
Q1, Q3				
Range				
Gender				
Male				
Female				

Table 2: Feasibility and Acceptability

Characteristic	Arm 1: Intervention Group 1	Arm 2: Intervention Group 2	Arm 3: Control (Usual Care)	Total N=

	(Blueprint + Blueprint Therapist) N=		N=
	N=	N=	
Feasibility			
% Consented	--	--	--

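### CSQ-8 acceptability is scored only in patients still in the study when the form is given, the documents disagree on when that is, and unscored app-arm patients play no part in the conclusion

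*Protocol*

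**What the plan says.** **Instrument and timing.** CSQ-8 is the acceptability part of the primary outcome. Protocol section 4 says: "The Client Satisfaction Questionnaire 8 will measure acceptability with open-ended participant feedback completed at the time of T3". Protocol section 3 agrees and lists it at T3 only: "Complete the HADS, PTSS, and PHQ-10, QOL 100-point visual analog scale, IADL/ADLs, CSQ-8". The survey forms in Appendix 3 differ. The T2 survey carries eight satisfaction items (103 to 110), beginning "How would you rate the quality of the Blueprint program", followed by free-text item 111: "Could you provide any comments about specific ways the Blueprint program helped or didn't help you". The T3 survey has neither. After the attention items it closes with "102. Click Next to submit your answers and see your results".

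**Analysis.** Protocol section 9 compares observed values with prespecified benchmarks among those who received mCST, using t-tests for continuous measures. SAP 4.1 says: "To assess Aim 1 for feasibility and acceptability we will evaluate CSQ-8 and SUS scores". SAP 3.1 gives CSQ-8 no time point and no benchmark. It sets retention at 80% and notes that the feasibility benchmarks still need sharper definition.

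**Patients who leave.** Of withdrawn and lost patients, Protocol section 7 (Screening, Recruitment and Consent) says: "Patients who reach this status have no additional follow-ups or study requirements". SAP 2.2 removes post-withdrawal data. Protocol section 5 and SAP 2.2 both list not opening the app within a month of randomisation as an exclusion. For a patient who asks to leave, Protocol section 12 (Withdraw While in Study) says: "A follow-up question may be asked to ascertain the reason for withdraw". It limits that answer to documentation. Neither document has a rule for a missing CSQ-8 in the acceptability conclusion.

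**The concern.** A satisfaction score taken late, and only from those still present, can favour the programme. If people who dislike the app leave before the form is given, the mean is computed without them, and losing more of them would raise it.

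The protocol's own rules connect low engagement to exit. Protocol section 7 lets the investigator withdraw a patient for continuing non-compliance, and it defines loss to follow-up as non-compliance plus at least three failed contacts. The post-randomisation exclusion for not opening the app removes the least engaged patients directly.

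The stake is one half of the primary hypothesis, that mCST is feasible and acceptable, in a pilot whose purpose is to inform the definitive trial.

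**Working it through.** The plan has no figure of its own to reproduce. It gives no CSQ-8 benchmark, no expected dropout and no derivation of the sample size.

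**Inputs**
- Retention target: 80% (SAP 3.1). Time point and denominator are not defined.
- App-arm patients: 25 + 25 = 50 (Protocol section 2), or 15 + 15 = 30 (SAP section 2).
- CSQ-8: eight items with four options each (T2 form). Assuming items are scored 1 to 4, the total runs from 8 to 32.
- Gap D, the mean of scored minus the mean of unscored patients: not in the documents. Assumed 0 to 8 points.
- SD of CSQ-8: not in the documents. Assumed 4 to 6.

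**Step 1. Unscored at T3 if app-arm retention is exactly 80%.** Share d = 1 - 0.80 = 0.20. That is 0.20 x 50 = 10 patients (protocol) or 0.20 x 30 = 6 (SAP). Patients excluded for not opening the app may come on top of this, because the retention denominator is undefined.

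**Step 2. Unscored if the form is given at T2.** Only losses before T2 count. If a fraction f of the 20% falls before T2, then d = 0.20 x f.

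| f | d | of 50 | of 30 |
|---|---|---|---|
| 0.25 | 0.05 | 2.5 | 1.5 |
| 0.50 | 0.10 | 5 | 3 |
| 0.75 | 0.15 | 7.5 | 4.5 |
| 1.00 | 0.20 | 10 | 6 |

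**Step 3. Bias in the mean.** The mean over all patients is (1 - d) x (scored mean) + d x (unscored mean). The scored mean exceeds it by d x D.

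| d | D = 0 | D = 4 | D = 8 |
|---|---|---|---|
| 0.05 | 0 | 0.2 | 0.4 |
| 0.10 | 0 | 0.4 | 0.8 |
| 0.15 | 0 | 0.6 | 1.2 |
| 0.20 | 0 | 0.8 | 1.6 |
| 0.30 | 0 | 1.2 | 2.4 |

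The sign depends on D: at d = 0.20, D = -4 gives -0.8. The scale maximum, D = 32 - 8 = 24, gives 4.8.

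**Step 4. Comparison with the reported precision.** The 95% half-width is t x SD / sqrt(n).
- n = 50 - 10 = 40: 1.28 at SD 4 and 1.92 at SD 6.
- n = 30 - 6 = 24: 1.69 at SD 4 and 2.53 at SD 6.

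At 20% loss and a gap of 8, the bias of 1.6 is about the size of the half-width, and the confidence interval would not show it.

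**Step 5. Can SUS fill the gap?** SAP 3.1 lists SUS at T1. T1 is completed before randomisation (Protocol section 7, Study Visits), so it cannot reflect experience of the assigned programme. No SUS items appear in the T1 to T3 forms, and SAP Table 2 lists only the CSQ score under acceptability.

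**The case against.** Much of the opposing case stands.

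- **Timing.** A reader of Protocol section 4 alone might infer that satisfaction is asked only at the end of follow-up. If the forms govern, it is asked at about the end of the 28-day programme, and patients lost between T2 and T3 are scored.
- **Quitting the app.** A reader might infer that anyone who abandons the programme goes unscored. Protocol section 3 says only that the team may contact a patient who stops using the app, and Protocol section 12 expects missed practices and does not count them as deviations. Such a patient can still answer T2 and T3. Withdrawal for non-compliance is discretionary.
- **The 20%.** This is the loss if an undefined target is just met. It is neither a ceiling nor an accepted loss.
- **Direction.** Patients also leave through death, readmission (which leads to withdrawal) and active suicidality needing immediate treatment. None of these is dislike of the app, and the gap is assumed. An upward bias is not demonstrated.
- **Visibility.** SAP section 4 already reports missing counts for each variable. SAP Table 2 shows retention and survey completion by arm beside the CSQ score, and retention and adherence have their own benchmarks. The joint hypothesis therefore does not rest on completers alone: heavy loss would show on the feasibility side.

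Reporting the loss does not, however, carry it into the acceptability conclusion. Nor do the forced responses in Protocol section 14: they prevent skipped items within a survey, not missed surveys or exits.

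**Conclusion.** The point holds in limited form. The CSQ-8 result comes from patients still present when the form is given, the documents contradict each other on when that is, and stated rules leave earlier leavers and never-users unscored. Because non-compliance is a route to exit, the least engaged app users are more likely to be missing, and the mean is plausibly too high.

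At T3, with app-arm retention exactly 80%, 10 of 50 or 6 of 30 are unscored and the overstatement is 0 to 1.6 points for an assumed gap of 0 to 8. At T2, with half the loss before it, the overstatement is 0 to 0.8. These figures rest on 1-to-4 item scoring and an assumed gap. Whether they would change the conclusion cannot be judged, because no CSQ-8 benchmark is stated.

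The documents do not support saying that the mean is certainly inflated, or that everyone who stops using the app is unscored. The change is worth making because it is cheap and concerns a primary outcome; it does not invalidate the design.

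**What to change.** 1. **Time point, benchmark, denominator.** Reconcile Protocol sections 3 and 4 with the T2 and T3 forms. State the CSQ-8 benchmark. Make all patients randomised to Arms 1 and 2 the denominator, including those who never opened the app, and define retention on a stated basis.
2. **Exit scores.** Amend the status definitions in Protocol section 7 and the Withdraw While in Study text in section 12, which now allows a question for documentation only. Offer the eight items at the withdrawal contact to app-arm patients who agree, and exempt these scores from the SAP 2.2 exclusion, which would otherwise discard them. Patients lost to contact cannot be reached this way, so item 3 is still needed.
3. **SAP 4.1.** Beside the mean, show the number unscored by arm and reason. Add a sensitivity analysis over a range of scores, down to the lowest, for app-arm patients unscored through voluntary withdrawal, non-compliance (including never opening the app) or loss to follow-up. Leave out deaths, readmissions and safety withdrawals, which do not signal dissatisfaction. State whether the conclusion against the benchmark survives.

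The range matters because the lowest score alone is severe. With an assumed scored mean of 26 and 20% set to 8, the mean becomes 0.8 x 26 + 0.2 x 8 = 22.4, a fall of 3.6.

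The cost is eight optional items at exit, short amendments to both documents, one extra analysis, and a less favourable lower bound.
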